## **10. SAFETY AND TOLERABILITY ANALYSIS**

The safety analysis will be run on the Safety population. The analysis of safety assessments in this study will include summaries of the following safety and tolerability data collected for each participant:

- Adverse Events
- Clinical Laboratory Investigations
- C-SSRS
- Vital Signs
- Visual Examinations of Oral Cavity
- Electrocardiogram (ECG) Parameters (Obtained at Screening only)
- Assessment of Morning Sedation (via MTRSS)
- Changes from baseline in participant-rated CSFQ-14
- BDI-II

Summaries of continuous parameters will include raw values and change from baseline, as appropriate. Listings of safety data will also be presented.

### **10.1 Adverse Events**

All AEs, treatment-emergent adverse events (TEAEs), and SAEs will be coded using MedDRA, version 19.0.

TEAEs are defined as either new onset AEs with an onset at the time of or following the start of treatment through ten days after the last dose of study medication, or a recurrence of an AE (or medical history) present prior to randomization but increasing in severity, frequency or relationship at the time of or following the start of treatment

An AE summary table will be presented for the following:

- TEAEs by severity
- TEAEs leading to study drug discontinuation
- TEAEs by relationship
- SAEs

Summaries of incidence rates (frequencies and percentages) of individual AEs by MedDRA SOC and preferred term will be prepared. Such summaries will be displayed for all TEAEs, TEAEs by maximum severity, and TEAEs by strongest relationship to study drug.

Each participant will be counted only once within each summation level (SOC; preferred term). If a participant experiences more than one TEAE within each summation level only, the TEAE with the strongest relationship or the maximum severity, as appropriate, will be included in the summaries of relationship and severity.

Adverse events of special interest pertaining to abuse potential (as defined in the January 2017 Assessment of Abuse Potential for Drugs – Guidance for Industry) will be analyzed separately by treatment group, SOC and preferred term, and displayed in tabular format.

In the AE data listings, all AEs will be displayed. AEs that are treatment-emergent will be flagged.

### **10.1.1 Adverse Events Leading to Discontinuation of Study Drug**

A summary of incidence rates (frequencies and percentages) of TEAEs leading to discontinuation of study drug by treatment group, SOC, and preferred term will be prepared for the Safety population.

A data listing of AEs leading to discontinuation of study drug will also be provided, displaying details of the event(s) captured on the CRF.

### **10.1.2 Serious Adverse Events**

A summary of incidence rates (frequencies and percentages) of SAEs by treatment group, SOC, and preferred term will be prepared for the Safety population. A data listing of SAEs will also be provided, displaying details of the event(s) captured on the CRF.

### **10.1.3 Deaths**

A listing of deaths will also be provided for the Safety Population.

## **10.2 Clinical Laboratory Evaluations**

Laboratory data include analyses for Chemistry and Hematology and will be summarized by treatment and visit for the Safety Population. Descriptive summaries of actual values and changes from baseline will be presented by study visit and each treatment group. 95% confidence intervals will be presented for change from baseline for each visit and last on-treatment assessment. ET data will be analyzed with the closest visit that does not have a valid assessment value.

Laboratory values will be displayed in the data listings and those that are outside the normal range (“H” or “L”) will be flagged, along with corresponding normal ranges. Values pre-defined as potentially clinically significant (“HH” or “LL”) will also be flagged. For each laboratory analysis, shifts in assessments of abnormality from baseline to each scheduled time point will be presented in shift tables.

A by-participant listing of all clinical laboratory data will also be provided.

## **10.3 Columbia Suicide Severity Rating Scale (C-SSRS)**

The C-SSRS is an instrument that measures suicidal ideation and behavior. Items measuring suicidal ideation and suicidal behavior are displayed in the table below. Frequency counts of yes/no responses to items below and whether any suicidal ideation or behavior is present will be summarized as described below.

The overall number of participants with lifetime and/or recent (past 6 months) suicidal ideation (by item, e.g., Ideation Types 1-5), and lifetime and/or recent (past 12 months) suicidal behavior (by item; e.g., Preparatory Act, Aborted Attempt, Interrupted Attempt, Actual Attempt and Completed Suicide), or non-suicidal self-injurious behavior at the screening and baseline visit will be summarized by visit and treatment group. Additionally, the overall number of participants with any suicidal ideation or behavior (by type and in total) or self-injurious behavior while on-treatment will be provided by

treatment group. For ideation, participants will only be counted once at each visit and/or time frame at the worst case response for ideation type (1-5), where 1 is the least severe and 5 is the most severe type of ideation.

Category	Items
A) Suicidal Ideation	(1) Type 1: Wish to be dead (2) Type 2: Non-specific active suicidal thoughts (3) Type 3: Active suicidal ideation with any methods (not plan) without intent to act (4) Type 4: Active suicidal ideation with any some intent to act, without specific plan (5) Type 5: Active suicidal ideation with specific plan and intent
B) Suicidal Behavior	(1) Preparatory acts or behavior (2) Aborted attempt (3) Interrupted attempt (4) Actual attempt (5) Completed suicide Suicidal Behavior present (composite of items 1-5) Non-Suicidal Self-Injurious Behavior

Suicidal intensity of ideation will be calculated by tallying up the five intensity items to create a total score ranging 0-25. If a participant does not have any suicidal ideation, a score of 0 will be given. Separate tables will be created for the entire Safety Population as well as the population comprising only participants exhibiting any suicidal ideation. Suicidal intensity of ideation total score will be summarized using descriptive statistics by treatment group.

A data listing of C-SSRS results will include only participants with suicidal ideation, suicidal behavior, or self-injurious behavior without suicidal intent. For participants with suicidal ideation, suicidal behavior, or self-injurious behavior without suicidal intent at any time, data from all visits are displayed.

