The primary efficacy analysis will use a mixed model repeated measures (MMRM) approach to estimate mean change from baseline in the Total CAPS-5 score evaluated after 12 weeks of treatment in the TNX-102 SL 5.6 mg and placebo arms. The model will include all patients in the mITT population, and missing values will be imputed using a multiple imputation (MI) approach. The dependent variable will be the observed change from baseline in total CAPS-5 score at each post-randomization visit. Covariates in the model will include the fixed categorical effects of treatment, site, sex, current tobacco use status, presence of current MDE, visit and treatment by visit interaction, as well as the continuous fixed covariates of baseline score and baseline score by visit interaction.

MMRM methodology will be utilized for the secondary endpoints as appropriate. Binary data, e.g., CGI-I response, will be analyzed using a Cochran-Mantel-Haenszel (CMH) test controlling for the randomization stratification variable of presence of current MDE, analyzed separately at each visit. Patients with missing data will be analyzed as though they are non-responders for binary endpoints. A fixed sequence procedure will be applied to the key secondary efficacy endpoints to adjust for multiplicity and to control for overall type I error.

Safety Analyses

Adverse events will be coded using the Medical Dictionary for Regulatory Activities (MedDRA) version in use at the start of the study and will be summarized overall and by preferred term and system organ class. Adverse events will also be summarized by severity and relationship to study drug. Serious AEs and AEs leading to discontinuation of study drug will also be summarized. Actual values and changes from Baseline for clinical laboratory test results, vital sign measurements, BDI-II scores, CSFQ-14, and morning sedation scores from the MTRSS will be summarized at endpoint using descriptive statistics (n, mean, SD, median, minimum, and maximum).

The number of patients with screening, baseline and treatment-emergent suicidal ideation and/or behavior, based on the C-SSRS will be summarized by treatment group.

Interim Analysis

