8.3. Exclusion Criteria

Eligible patients who meet any of the following criteria during the screening period should be excluded from the study:

1. Increased risk of suicide on the basis of the investigator's judgment and/or the results of the Mini International Neuropsychiatric Interview, Version 7.0.2 (M.I.N.I. 7.0.2) conducted at Screening and the Columbia Suicide Severity Rating Scale (C-SSRS) conducted at Screening and/or Baseline. Any of the following will be exclusionary:
 - a. High suicidality based on a M.I.N.I. Module B score ≥ 17 (Screening); or,
 - b. Patient answers YES to either M.I.N.I. question B10 or B11 (Screening); or,
 - c. Patient meets criteria for CURRENT Suicidal Behavior Disorder on the M.I.N.I (Screening); or,
 - d. C-SSRS Type 4 or Type 5 ideation within 6 months of Screening or at the Baseline visit; or,
 - e. Any suicidal behavior in the past 12 months as identified by the C-SSRS at Screening or Baseline.
2. Increased risk of suicide, based on the investigator's judgment that is of a severity that is not appropriate for outpatient management, or that warrants additional therapy excluded by the protocol.

3. Significant (e.g., moderate or severe) comorbid traumatic brain injury (TBI) by history. Based on past history and investigator's judgment, patients with mild TBI are eligible.
4. Evidence of severe depression at screening or baseline (Visits 1 or 2) based on the investigator's judgment and collaborative pre-randomization review by the investigator and medical monitor(s) of the patient's psychiatric history, presenting symptomatology, M.I.N.I. 7.0.2 (including Major Depressive Episode and Suicidality modules), C-SSRS, CAPS-5, and BDI-II assessments.
5. Clinically significant laboratory abnormalities based on screening laboratory tests and/or medical history in the investigator's opinion, including a Thyroid Stimulating Hormone (TSH) level >1.5 times the upper limit of normal and aspartate aminotransferase (AST) and/or alanine aminotransferase (ALT) > 3 times the upper limit of normal (if persistent upon repeat). Patients with treated thyroid conditions and TSH levels ≤ 1.5 times the upper limit of normal will be eligible to participate in the study.
6. Diagnosed with clinically significant cardiac disease (e.g., significant arrhythmia or heart block, heart failure, or recent myocardial infarction [within the past 2 years]) or QTcF >450 msec (male) or >470 msec (female) on the screening electrocardiogram (ECG).

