13.5. Safety Analyses

Safety will be assessed by:

- Adverse events and serious AEs throughout the entire duration of the study, including assessment of AEs involving the oral cavity

- Changes from baseline in clinical laboratory test results
- Changes from baseline in vital signs and weight
- Changes from baseline indicative of increased suicidal ideation or behavior as assessed by the C-SSRS
- Changes from baseline in BDI-II
- Changes from baseline in patient-rated sexual function as assessed by the CSFQ-14
- Changes from baseline in patient-rated morning sedation as assessed by the MTRSS

Adverse events will be coded using the latest version of MedDRA and will be summarized overall and by preferred term and system organ class. Adverse events will also be summarized by severity and relationship to study drug. Serious AEs and AEs leading to discontinuation of study drug will also be summarized. Actual values and changes from Baseline for clinical laboratory test results, MTRSS scores, CSFQ-14 scores, BDI-II scores, and vital sign measurements will be summarized at endpoint using descriptive statistics (n, mean, SD, median, minimum, and maximum).

The number of patients with suicidal behaviors, ideations and acts based on the C-SSRS will be tabulated by treatment group and listed.

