### **2.2.3 Safety Endpoints**

Safety will be assessed by:

- Adverse events (AE) and serious AEs (SAEs) throughout the entire duration of the study, including detailed assessment of AEs involving the oral cavity.
- Changes from baseline in clinical laboratory test results.
- Changes from baseline in vital signs and weight.
- Change from baseline in BDI-II.
- Changes from baseline in suicidal ideation or behavior as reported on the Columbia Suicide Severity Rating Scale (C-SSRS).
- Changes from baseline in participant-rated Changes in Sexual Functioning Questionnaire Short-Form (CSFQ-14).
- Changes from baseline in participant-rated morning sedation as assessed by the Morning Treatment-Related Sedation Score (MTRSS).

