### 7.3 Safety Assessments

Safety will be assessed by:

- AE and SAEs throughout the entire duration of the study, including detailed assessment of AEs involving the oral cavity.
- Changes from baseline in clinical laboratory test results.
- Changes from baseline in vital signs and weight.
- Change from baseline in BDI-II (see Section 7.2.4).
- Changes from baseline indicative of increased suicidal ideation or behavior as assessed by the C-SSRS.
- Changes from baseline in participant-rated CSFQ-14.
- Changes from baseline in participant-rated morning sedation as assessed by the MTRSS.

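### SAP 10.3 plans no C-SSRS summary by arm that compares participants with their own baseline, although the protocol synopsis calls for treatment-emergent counts

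*SAP*

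**What the plan says.** **The commitments.** The protocol synopsis, under its safety analyses, says: "The number of patients with screening, baseline and treatment-emergent suicidal ideation and/or behavior, based on the C-SSRS will be summarized by treatment group". Protocol 7.3.4 and 13.5 list C-SSRS changes from baseline that indicate an increase as a safety measure. SAP 7.3 repeats this: "Changes from baseline indicative of increased suicidal ideation or behavior as assessed by the C-SSRS". SAP 2.2.3 also names change from baseline, without the reference to an increase.

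**The tabulation sentence in the protocol body.** Protocol 13.5 is looser than the synopsis: "The number of patients with suicidal behaviors, ideations and acts based on the C-SSRS will be tabulated by treatment group and listed". It does not use the term treatment-emergent.

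**The planned analysis.** SAP 10.3 has three by-arm elements:
- counts of ideation and behavior, by item, at screening and baseline;
- an on-treatment count: "the overall number of participants with any suicidal ideation or behavior (by type and in total) or self-injurious behavior while on-treatment will be provided", with ideation counted at the worst type;
- descriptive statistics for a 0-25 ideation-intensity total.

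It adds a listing of all visits for any participant with ideation, suicidal behavior or self-injury. It defines no treatment-emergent category and plans no shift table. The only change declared in SAP Section 12 is the Day 0/Day 1 numbering.

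**Entry.** Protocol 8.3, criterion 1d, excludes "C-SSRS Type 4 or Type 5 ideation within 6 months of Screening or at the Baseline visit". Criterion 1e excludes suicidal behavior in the past 12 months. No criterion excludes Types 1-3 by type.

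**The concern.** The stated safety measure is an increase from baseline, but no planned by-arm table measures one for Types 1-3. A participant with Type 2 at baseline and Type 2 at Week 4 enters the on-treatment table exactly as one who goes from none to Type 2. One who goes from Type 1 to Type 3 appears in the Type 3 row, but nothing marks this as a worsening.

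The documents lead one to expect some baseline ideation. Patients with depression may enter, current major depressive episode is a randomization factor, and Protocol 7.1 and 11.3.3 provide a safety-planning step for Type 2 or 3 scores at any visit, including Screening.

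The SAP uses baseline-referenced methods elsewhere: shift tables for laboratory values (10.2) and a treatment-emergent definition for adverse events (10.1). What is at stake is how clearly a reader can see a difference between arms in new or worsening ideation.

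**Working it through.** The documents give no C-SSRS rates, so there is no figure to reproduce. Apart from the arm size, every rate below is an assumption.

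**Step 1: the texts side by side**

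| Item | Referenced to baseline? |
|---|---|
| Synopsis: treatment-emergent counts | Yes |
| Protocol 7.3.4 and 13.5, SAP 2.2.3 and 7.3: change from baseline | Yes |
| Protocol 13.5: tabulation sentence | No |
| SAP 10.3: screening/baseline counts and on-treatment counts | No; separate counts, not crossed |

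**Step 2: formulas.** Let b be the proportion with Type 1-3 ideation at baseline, q the share of these with ideation on treatment, w the share of those persisters who reach a higher type, and n the new-onset rate among participants with none at baseline.

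- Any on treatment (the total row) = bq + (1 - b)n
- Treatment-emergent = (1 - b)n + bqw

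Randomization makes b equal in expectation. If q and w are also equal between arms, both counts have the same risk difference, (1 - b)(n1 - n0). The ratio is smaller for the first count because bq is added to both arms.

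**Step 3: rise as new onset only (w = 0, equal q)**

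| b | q | n, placebo v drug | Any on treatment | Ratio | Emergent | Ratio | Difference, both counts |
|---|---|---|---|---|---|---|---|
| 10% | 50% | 2% v 5% | 6.8% v 9.5% | 1.40 | 1.8% v 4.5% | 2.50 | 2.7 points |
| 5% | 50% | 4% v 10% | 6.3% v 12.0% | 1.90 | 3.8% v 9.5% | 2.50 | 5.7 points |
| 20% | 80% | 4% v 10% | 19.2% v 24.0% | 1.25 | 3.2% v 8.0% | 2.50 | 4.8 points |
| 40% | 80% | 4% v 10% | 34.4% v 38.0% | 1.10 | 2.4% v 6.0% | 2.50 | 3.6 points |

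Third row in full: 0.20 x 0.80 = 0.160; 0.80 x 0.04 = 0.032; 0.80 x 0.10 = 0.080. So any is 0.192 v 0.240 and emergent is 0.032 v 0.080.

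Precision for that row with 275 per arm (SAP Section 5), as the standard error of the difference:
- any: sqrt[(0.192 x 0.808 + 0.240 x 0.760)/275] = 3.5 points
- emergent: sqrt[(0.032 x 0.968 + 0.080 x 0.920)/275] = 1.95 points

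**Step 4: rise only as worsening in those who already have ideation** (b = 30%, q = 80%, n = 4% in both arms, w = 10% v 30%)
- any: 0.240 + 0.028 = 26.8% in both arms, ratio 1.00
- emergent: 0.028 + 0.024 = 5.2% v 0.028 + 0.072 = 10.0%, ratio 1.92, about 14 v 28 participants of 275

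Across b = 10% to 40% the emergent ratio runs from 1.36 to 2.14. The total row shows nothing; the by-type rows would show part of the shift.

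**Step 5: drug raises new onset (4% to 10%) and lowers persistence (80% to 50%)**
- b = 30%: any is 0.240 + 0.028 = 26.8% v 0.150 + 0.070 = 22.0%, ratio 0.82. New onset as a share of the whole arm is 2.8% v 7.0%.
- b = 10%: any is 11.6% v 14.0%, ratio 1.21, so the rise still shows.

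**The case against.** The strongest case against has five parts.

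1. *Treatment-emergent* appears for the C-SSRS only in the synopsis, undefined, and SAP 10.3 does what the tabulation sentence in Protocol 13.5 asks. This is correct, but Protocol 13.5 also lists increase from baseline as the measure, and the SAP repeats change from baseline twice. The mismatch stands.

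2. A reader might infer that persistent ideation hides a rise caused by the drug. The documents do not support that. Step 3 shows that the absolute excess survives when persistence is equal. Masking needs the conditions of Step 4, and then only in the total row, or a sufficient fall in persistence as in Step 5.

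3. A reader might add that the planned table lacks power. No test of it is planned: SAP 10.3 is descriptive, and SAP 7.1.1.1 makes p-values outside the testing sequence descriptive only. The point needs no power claim.

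4. Entry screening is broader than the Type 4-5 rule. Protocol 8.3 also excludes on M.I.N.I. suicidality (Module B score of 17 or more, a positive B10 or B11, current Suicidal Behavior Disorder), on investigator judgment of suicide risk, and on severe depression. This stands: baseline ideation could be near the low end of the assumed range.

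5. Other outputs cover part of the gap.
   - The by-type counts are by arm, but do not show whether a type is new.
   - The all-visit listing shows each change, but is not a by-arm summary.
   - Under Protocol 11.3.3, Type 4-5 at a clinic visit is a serious adverse event, and a significant change to Type 2-3 is an adverse event. Both reach by-arm tables, but the second rests on judgment and new Type 1 is not covered.
   - SAP Section 10 allows change from baseline for continuous parameters where appropriate; for the intensity total, 10.3 does not specify it.

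   These outputs soften the concern without closing it.

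**Conclusion.** The concern holds as an undeclared gap between the stated safety measure and the planned summary, confined in practice to Type 1-3 ideation. This rests on the texts alone and needs no assumed rate.

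The consequence is moderate. With equal persistence, the planned count keeps the risk difference and dilutes the ratio and precision: 1.10 to 1.90 against 2.50 in the 4% v 10% rows of Step 3. Masking is possible under narrower assumptions but does not follow from the plan. The true baseline prevalence and persistence are unknown from the documents.

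On-treatment Type 4-5 ideation and suicidal behavior are little affected. Recent cases are excluded at entry, so almost any occurrence is new relative to the entry look-back.

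**What to change.** Amend SAP 10.3 and keep the planned counts:

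1. **Definitions.** Treatment-emergent ideation: worst on-treatment type higher than worst pre-treatment type, with none as the lowest category. Split it into new onset (none before treatment) and worsened (some before, higher type on treatment). New-onset behavior: behavior on treatment with none in the pre-treatment look-back.
2. **Look-back.** For ideation, use the Visit 1 past-6-month recall plus the Visit 2 since-last-visit assessment. Repeat with Visit 2 alone, because the recall periods differ: a longer window can only raise the pre-treatment worst type and so lower the emergent count. State the corresponding look-back for behavior, where the Visit 1 recall is one year.
3. **Tables by arm.** (a) A shift table of worst pre-treatment against worst on-treatment type (none, Types 1-5). (b) Counts of new-onset ideation, worsened ideation and new-onset behavior.

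If the sponsor prefers not to add these, SAP Section 12 should record the departure from the synopsis.

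The cost is SAP wording and two descriptive tables. The C-SSRS is already administered at every visit (Protocol 11.3.2 and Appendix 1), so no new data, visits or tests are needed.

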#### 10.4 Vital Signs

Descriptive summaries (mean, SD, median, minimum, and maximum) of actual values and changes from baseline at each assessment time point and last on-treatment assessment will be calculated for vital signs including weight, BMI, body temperature, pulse rate, systolic blood pressure and diastolic blood pressure. 95% confidence intervals will be presented for change from baseline.

These summaries will be presented by treatment and assessment time for the Safety population. ET data will be analyzed with the closest visit that does not have a valid assessment value.

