Cyclobenzaprine relieves skeletal muscle spasm of local origin without interfering with muscle function. Cyclobenzaprine has not been shown to be effective in muscle spasm due to central nervous system disease. In animal models, cyclobenzaprine reduced or abolished skeletal muscle hyperactivity. Animal studies indicate that cyclobenzaprine does not act at the neuromuscular junction or directly on skeletal muscle. Such studies show that cyclobenzaprine acts primarily within the central nervous system at the brain stem as opposed to the spinal cord level, although an overlapping action on the latter may contribute to its overall skeletal muscle relaxant activity. Evidence suggests that the net effect of cyclobenzaprine is a reduction of tonic somatic motor activity, influencing both gamma (γ) and alpha (α) motor systems. Pharmacological studies in animals demonstrated a similarity between the effects of cyclobenzaprine and the structurally related tricyclic antidepressants, including reserpine antagonism, norepinephrine potentiation, potent peripheral and central anticholinergic effects, and sedation. Cyclobenzaprine caused slight to moderate increase in heart rate in animals.

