## **7. GENERAL ISSUES FOR STATISTICAL ANALYSIS**

### **7.1 General Statistical Methodology**

Descriptive summaries will be provided where appropriate for each of the primary and secondary variables. In general, tables will summarize data by treatment group and visit.

Baseline characteristic and safety tables will be completed for the Safety Population unless otherwise specified. Efficacy tables will be presented for the mITT Population.

Continuous, quantitative, variable summaries will include the number of participants (N) with non-missing values, mean, standard deviation (SD), median, minimum, and maximum.

Categorical, qualitative, variable summaries will include the frequency and percentage of participants who are in the particular category. In general, the denominator for the percentage calculation will be based upon the total number of participants in the study population for the treatment group unless otherwise specified.

Baseline values are defined as the last non-missing measurement prior to the first dose of study drug. Change from baseline will be defined as the post-baseline visit value minus the baseline value.

ET participants will only be followed if required to monitor an on-going adverse event or other condition.

Participants are not supposed to change study sites; however, should this be necessary to allow a participant to continue in the study, participants will be analyzed under the site where they were initially enrolled.

Study day after first dose is defined as assessment date – first dose date +1. Dates prior to first dose are defined as assessment date – first dose date. Note that the protocol refers to “Day 0”; for the purposes of the datasets and analyses, this would appear as day 1.

All analyses will be performed using Statistical Analysis System (SAS®) Software version 9.3 or later.

Alpha levels are discussed in [Section 7.1.1.2](#) below; unless otherwise noted, 95% confidence intervals will be presented for statistical tests.

Presence of current tobacco/nicotine use and MDE is recorded first in the Interactive Web Response System (IWRS) during screening for purposes of randomization stratification and, after randomization, transcribed into the electronic data capture (EDC) system (as part of substance use history and the results for the MINI). The source for tobacco/nicotine use MDE in all analyses and statistical models will be the EDC data and not the IWRS.

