### **10.8 Assessment of Changes in Sexual Function: Changes in Sexual Functioning Questionnaire Short-Form (CSFQ-14)**

The CSFQ-14 ([Keller et al. 2006](#)) is a validated scale with internal reliability designed to allow a participant to self-evaluate his or her sexual behaviors or problems in several areas. The CSFQ-14 will be administered at Baseline (Visit 2) and Week 12/ET (Visit 6). It yields a total score, three subscales corresponding to phases of the sexual response cycle (i.e. desire, arousal, orgasm), and five subscales corresponding to important dimensions of sexual functioning. It is considered a useful scale for assessing sexual side effects of medications. For all items, higher scores reflect higher sexual functioning. For

12 of the 14 items, higher sexual functioning corresponds to greater frequency or enjoyment/pleasure (e.g. 1=never to 5 = every day). For two items (item 10, assessing loss of interest after arousal for women and priapism for men, and item 14, assessing painful orgasm), higher sexual functioning corresponds to lower frequency (e.g. 1=every day to 5=never). Items 10 and 14 are included in the total score but not in any scale score.

Descriptive summaries (mean, SD, median, minimum, and maximum) of actual values and changes from baseline at each assessment time point will be reported.

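### Vital-sign and laboratory changes get per-arm confidence intervals only; no TNX-102 SL minus placebo difference with an interval is planned

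*SAP*

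**What the plan says.** SAP 10.4 plans descriptive summaries of actual values and changes for weight, BMI, temperature, pulse and blood pressure, and adds that "95% confidence intervals will be presented for change from baseline". On layout it says: "These summaries will be presented by treatment and assessment time for the Safety population".

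SAP 10.2 does the same for chemistry and hematology: "Descriptive summaries of actual values and changes from baseline will be presented by study visit and each treatment group", and "95% confidence intervals will be presented for change from baseline for each visit and last on-treatment assessment". It also plans shift tables: "For each laboratory analysis, shifts in assessments of abnormality from baseline to each scheduled time point will be presented in shift tables".

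SAP 7.1 fixes the quantity that the interval describes: "Change from baseline will be defined as the post-baseline visit value minus the baseline value". It is therefore a within-participant change. The SAP does not use the term within-arm; that reading follows from this definition together with the by-treatment layout. SAP 7.1 otherwise ties 95% intervals to statistical tests, and no test is planned for these measures.

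Elsewhere the SAP does specify a between-arm interval. Section 9.1.1 plans 95% intervals for the CAPS-5 treatment difference at each time point. Protocol 13.5 plans only descriptive statistics for laboratory values and vital signs, so the intervals in SAP 10.2 and 10.4 are an addition made by the SAP.

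**The concern.** Safety is the trial's secondary objective, and participants are randomized 1:1 to placebo. For pulse, blood pressure, weight and laboratory values, the useful question is how much more the drug arm changed than the placebo arm, and with what uncertainty. A per-arm interval answers a different question: whether that arm moved from its own baseline.

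Some shared movement is plausible. Under the Protocol's Appendix 1 and Section 11.3.8, chemistry and hematology are drawn at Screening and again at Week 12 or early termination. The laboratory baseline therefore normally precedes washout of excluded drugs, and the change spans that washout in both arms. For vital signs the baseline is Visit 2, after a drug-free week for most excluded drugs, so the case for a shared change is weaker there.

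The measures matter for this compound. ECG is done at Screening only (SAP 10.6), so pulse and blood pressure carry much of the objective on-treatment cardiovascular information. The appended label (Protocol Appendix 3, mechanism of action) notes that "Cyclobenzaprine caused slight to moderate increase in heart rate in animals". That is animal data. It is a reason to look at pulse, not evidence of an effect in this trial.

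**Working it through.** The plan states no figure for these intervals, so there is none to reproduce. The inputs to the planned 550 are blacked out and are not needed here.

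**Inputs.** n = 275 per arm (SAP 5). For the early-stop case, about 137 per arm (assumption: an even split of the roughly 275 interim participants). SD units are used because the documents give no SD. The shared change d is an assumption, with a range.

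**What each interval estimates.** Let d be the change common to both arms and θ the drug effect. The TNX-102 SL interval estimates d + θ, the placebo interval d, and the difference θ. Only the difference is free of d.

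**Half-widths (normal approximation).**
- Within arm: 1.96/√n = 1.96/√275 = 0.118 SD; at 137, 0.167 SD.
- Between arms: 1.96·√(2/n) = 1.96·√(2/275) = 0.167 SD; at 137, 0.237 SD.

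**No drug effect (θ = 0).** The chance that one arm's interval excludes zero is p = Φ(d√n − 1.96) + Φ(−d√n − 1.96). For d = 0.20 and n = 275, d√n = 3.317 and p = Φ(1.357) = 0.91. The chance that exactly one of the two arms' intervals excludes zero is 2p(1 − p).

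| Shared change (SD) | p, n = 275 | Exactly one arm, n = 275 | p, n = 137 | Exactly one arm, n = 137 | Difference interval |
|---|---|---|---|---|---|
| 0.10 | 0.38 | 0.47 | 0.22 | 0.34 | 0.05 |
| 0.15 | 0.70 | 0.42 | 0.42 | 0.49 | 0.05 |
| 0.20 | 0.91 | 0.16 | 0.65 | 0.46 | 0.05 |
| 0.30 | >0.99 | <0.01 | 0.94 | 0.11 | 0.05 |

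**In natural units** (assumed: 200 to 260 evaluable per arm, SD of change 10 bpm for pulse and 3 kg for weight). With no drug effect, the drug-arm interval excludes zero in 11–13%, 29–36% and 80–90% of trials for shared pulse drifts of 0.5, 1 and 2 bpm. For shared weight drifts of 0.25 and 0.5 kg the figures are 22–27% and 65–76%.

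**The opposite error.** With a true effect of +3 bpm and a shared drift of −3 bpm, the drug-arm interval excludes zero in 5% of trials. The difference interval does so in 85–93%: at n = 200, 3/(10·√(2/200)) = 3.0 and Φ(3.0 − 1.96) = 0.85.

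**Looking for overlap instead.** Two arm intervals at n = 275 separate only when the means differ by more than 2 × 0.118 = 0.236 SD. The difference interval already excludes zero beyond 0.167 SD. Differences between those two values would look compatible with no effect when judged by overlap.

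**Limit of the remedy.** The difference interval excludes zero with probability 0.22, 0.65 or 0.94 for a true difference of 0.10, 0.20 or 0.30 SD at 275 per arm, and 0.13, 0.38 or 0.70 at 137.

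**The case against.** The strongest defence is that placebo appears in the same table. In the cancellation example, placebo falls by 3 bpm and its own interval excludes zero in about 99% of trials, so an attentive reader sees roughly 0 against −3. Each arm's n, mean and SD are tabulated, so an unadjusted difference and interval can be worked out by hand. All SDs, drifts and effects above are assumed, and exact cancellation is a chosen case. Descriptive safety reporting is what Protocol 13.5 provides for. All of this stands, and it limits the point to presentation: no information is lost. It does not rescue comparison of two within-arm intervals by eye, as the exactly-one-arm columns show.

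Several stronger inferences are tempting, and the documents do not support them.
- A reader might infer that the arms are not compared at all on safety. Both are displayed together, laboratory shift tables are planned, and adverse events are summarized by treatment group. BDI-II, a named safety endpoint, also gets a between-arm repeated-measures analysis at each visit (SAP 9.2.1).
- A reader might infer that the plan treats within-arm change as evidence about the drug. No text says so.
- A reader might cite the TSH entry limit as a source of regression to the mean. TSH is measured only at Screening and has no change score.
- A reader might extend the point to CSFQ-14. SAP 10.8 plans descriptive summaries there with no interval, so there is none to correct.

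**Conclusion.** The point holds as a weakness in how the safety data will be presented. For vital signs, weight, chemistry and hematology, the only planned intervals are per arm, and no drug-minus-placebo difference or interval is specified. Under assumed shared changes of 0.10 to 0.20 SD with 275 per arm and no drug effect, exactly one arm's interval excludes zero in 16% to 47% of trials, against 5% for the difference interval. The structural argument, that only the difference removes the shared change, does not depend on those assumptions; the percentages do. The primary CAPS-5 result and its type I error are unaffected, and the two documents do not contradict each other. The change should be made because it improves the answer to the secondary objective at little cost.

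**What to change.** In SAP 10.2 and 10.4, replace the sentences on confidence intervals with wording such as: *For each post-baseline visit and the last on-treatment assessment, the TNX-102 SL minus placebo difference in mean change from baseline, adjusted for the baseline value, will be presented with its two-sided 95% confidence interval. For strongly skewed analytes, named before unblinding, the unadjusted difference will be given. These intervals are descriptive, with no multiplicity adjustment.* Keep the per-arm summaries and the shift tables.

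Add a rule for an early stop. SAP 6 counts placebo participants who roll over to open-label drug under TNX-102 SL in the full Safety Population. The difference should then be computed in the Early Stop Safety Population, which excludes participants ongoing at the stop.

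**Cost.** No new data, visits or participants. There is some programming: six vital-sign measures, and 34 laboratory analytes by my count of Protocol Table 2 (16 chemistry, 18 hematology with each differential as absolute and percent). Some difference intervals will exclude zero by chance. Across 34 analytes at Week 12 with no drug effect, about 34 × 0.05 = 1.7 are expected to do so, which is why the descriptive label matters.
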